#### **Serious Adverse Reaction (SAR)**

A serious adverse reaction is an SAE that is suspected as having a causal relationship to the study intervention, as assessed by the investigator responsible for the care of the patient. A suspected causal relationship is defined as possibly, probably or definitely related (see definitions of causality table).

In PRIMETIME, the study intervention is considered to be the omission of radiotherapy.

#### **Definitions of causality**

Relationship	Description
Unrelated	There is no evidence of any causal relationship with the study intervention
Unlikely	There is little evidence to suggest there is a causal relationship (e.g. the event did not occur within a reasonable time of the study intervention). There is another reasonable explanation for the event (e.g. the patient's clinical condition, other concomitant treatment)
Possible	There is some evidence to suggest a causal relationship (e.g. because the event occurs within a reasonable time of the study intervention). However, the influence of other factors may have contributed to the event (e.g. the patient's clinical condition, other concomitant treatments)
Probable	There is evidence to suggest a causal relationship, and the influence of other factors is unlikely
Definitely	There is clear evidence to suggest a causal relationship, and other possible contributing factors can be ruled out
Not assessable	There is insufficient or incomplete evidence to make a clinical judgement of the causal relationship.

#### Related **Unexpected Serious Adverse** Event

An adverse event that meets the definition of serious and is assessed by the Chief Investigator or nominative representative as:

#### 11.2. Reporting of Serious Adverse Events to ICR-CTSU

All SAEs should be reported to ICR-CTSU within 24 hours of the Principal Investigator (or designated representative) becoming aware of the event, by completing the PRIMETIME SAE form and faxing to:

The ICR-CTSU safety desk
[contact]
For the attention of the PRIMETIME Study team

As much information as possible, including the Principal Investigator's assessment of causality, must be reported to ICR-CTSU in the first instance. Additional follow up information should be reported as soon as it is available.

"Related" - that is, it resulted from the research intervention, and

"Unexpected" – that is, the type of event judged as being related to the omission of radiotherapy that is not considered to be an expected occurrence by the Chief Investigator.

All SAE forms must be completed, signed and dated by the Principal Investigator or designated representative.

#### 11.3. Review of Serious Adverse Events

The Chief Investigator (or designated representative) will assess all reported SAEs for causality and expectedness (NB. The Chief Investigator cannot down-grade the Principal Investigator's assessment of causality.)

SAEs assessed as having a causal relationship to the study intervention and as being unexpected will undergo expedited reporting to the relevant authorities and all other interested parties by ICR-CTSU.

Sites should respond as soon as possible to requests from the Chief Investigator or designated representative (via ICR-CTSU) for further information that may be required for final assessment of an SAE.

#### 11.4. Expedited Reporting of Related Unexpected SAEs

If an SAE is identified as being related and unexpected by the Chief Investigator it will be reported by ICR-CTSU to the main REC, the Sponsor and all other interested parties within 15 days of being notified of the event.

The Principal Investigators at all actively recruiting sites will be informed of any related unexpected SAEs occurring within the study at appropriate intervals.

#### 11.5. Follow up of Serious Adverse Events

SAEs should be followed up until clinical recovery is complete or until disease has stabilised. SAE outcomes should be reported to ICR-CTSU using the relevant section of the SAE form as soon as the Principal Investigator or designee becomes aware of the outcome.

#### 11.6. Annual Safety Reporting

An annual progress report will be provided to the main REC by ICR-CTSU and copied to the Sponsor at the end of the reporting year. This will include data about related unexpected SAEs and whether any safety concerns have arisen during the reporting period.

Adverse event observed in trial participant Adverse event considered serious as defined Responsibilities of Participating Centre by the trial protocol? Νo Yes **IMMEDIATE REPORTING** No immediate reporting **COMPLETE STUDY SPECIFIC SAE FORM** Fax SAE form to ICR-CTSU within 24 hours of becoming aware of the event Sites must respond immediately to Receipt of SAE acknowledged by ICR-CTSU personnel and any requests for further information that missing / unclear data queried may be required for CI assessment ICR-CTSU forward SAE to the Chief Investigator (CI) or nominated representative for assessment of relatedness and expectedness. Return by fax to the ICR-CTSU once assessment is complete Responsibilities of (Co)Sponsor as per agreement Both the PI and CI PI and/or CI suspects suspect SAE is unrelated SAE is related CI (or nominated Related unexpected SAEs will be No further reporting representative) reported by required assessment of ICR-CTSU to: expectedness of the SAR Main Research Ethics Committee (Main REC) within 15 calendar days Expected Unexpected of initial report • Sponsor institutions Related unexpected SAR • Principal investigators at regular SAE ICR-CTSU report any intervals Requires expedited safety concerns to the reporting REC annually in their specified format. Sponsor institution also notified at agreed timelines Related unexpected SAEs Follow Up Additional relevant information reported to Main REC and Sponsor as soon as possible

Figure 3: Flow diagram for SAE reporting, and action following report

NB. All SAEs should continue to be followed up as specified above

#### 12. STATISTICAL CONSIDERATIONS

#### 12.1. Statistical Design and Sample Size Justification

The primary objective is to assess the safety of avoiding radiotherapy in terms of risk of ipsilateral breast disease. In the cohort of patients for whom selective avoidance of radiotherapy is advocated, the ipsilateral breast disease rate is expected to be ≤4% at 5 years. The sample size has been calculated based on excluding at most a 5% ipsilateral breast disease rate at 5 years within this group using a one-sided 97.5% confidence interval. Allowing for 5% of patients to be non-evaluable at the time of primary endpoint analysis (due to patients progressing with metastatic BC or dying from unrelated causes) gives a total of 1550 patients required in the no radiotherapy cohort.

It is expected approximately 70% of patients screened for PRIMETIME will be defined as very low risk using the IHC4+C score, and assuming a 7.5% non-compliance with the screening stage, 2400 patients will need to be screened to ensure sufficient numbers enter the no radiotherapy cohort. Therefore, it is estimated that approximately 660 patients who are screened for PRIMETIME will be advised to receive radiotherapy according to standard practice. These patients will provide an estimate (and 95%CI) of ipsilateral breast disease rates following radiotherapy in a largely low risk patient group (as opposed to a very low risk group) however they will not form a direct comparator group due to the inherent differences in their risk profile. For example, with 660 patients and 16 ipsilateral breast disease events, a 2.4% ipsilateral breast disease rate with 95% CI 1.4-3.9% can be estimated.

#### 12.2. Treatment Allocation

There is no randomised treatment allocation, all registered patients will be directed to receive radiotherapy or not depending on their IHC4+C assigned risk category. Patients with a <5% probability of local relapse at 10 years (very low risk) will be directed not to receive radiotherapy.

#### 12.3. Endpoint Definitions

#### 12.3.1. Primary endpoint

Any ipsilateral breast disease rate (defined as invasive and/or non-invasive disease (DCIS) in the ipsilateral breast).

#### 12.3.2. Secondary endpoints

- Regional relapse rate (regional relapse is defined as invasive relapse within the axilla, supraclavicular fossa and internal mammary chain)
- Distant relapse rate
- Ipsilateral invasive breast disease rate (defined as invasive disease in the ipsilateral breast)
- Contralateral invasive breast second primary cancer rate
- Any contralateral breast disease rate (defined as invasive and/or non-invasive disease (DCIS) in the contralateral breast).
- Ipsilateral invasive breast local relapse rate (subject to availability of tumour profiling data)
- Ipsilateral invasive breast second primary cancer rate (subject to availability of tumour profiling data)
- Invasive disease free survival defined as time from registration to first event where event can be any invasive local recurrence, regional recurrence, distant recurrence, second primary cancer or death from any cause.

- Breast cancer specific survival defined as time from registration to first event where event can be local recurrence, regional recurrence, distant recurrence, breast second primary or breast cancer death. Death from unknown cause would be classed conservatively as breast cancer death.
- Overall survival defined as time from registration to death from any cause

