	The Information Giving Study will identify if the introduction of a patient decision aid video in addition to written patient information reduces decisional conflict (patient uncertainty) regarding whether to participate in the PRIMETIME main study.
FOLLOW UP	Patients who do not receive radiotherapy (Surgery Only):
	
 
Patients should have annual mammography for 10 years.
 
Patients should attend follow up clinics according to local practice
 
ICR-CTSU will contact research sites annually to request an update on patient status.
 
Information on disease relapse will be collected at follow up clinics, by telephone call and by annual mammography and recorded in the PRIMETIME eCRF.
 

	Patients who receive radiotherapy:
	
 
Patients will have annual mammography according to local practice.
 
Patients will attend follow up clinics according to local practice.
 
ICR-CTSU will contact research sites annually to request an update on patient status.
 
Information on disease relapse will be collected at follow up clinics, by telephone call and by annual mammography and recorded in the PRIMETIME eCRF.
 

	Routine data linkage: In addition to the above, the study will establish mechanisms for collecting data (including local, distant relapse, new primary cancers, death, cause of death) directly from routinely collected health data. Routine data collection will be compared to the gold-standard centrebased follow-up, including identification of ipsilateral breast local relapse versus new ipsilateral breast second primary cancer. The relevant data sources proposed include the Cancer Services and Outcomes Dataset (COSD), the National Radiotherapy Dataset (RTDS), the Systemic Anti-Cancer Therapy Dataset (SACT), the Hospital Episodes Statistics (HES), the ONS mortality file, the equivalent databases in the devolved nations and any other UK informative registries.  Routine data linkage will performed for all patients (pre-screened for Ki67 and registered for the main study i.e. IHC4+C directed

treatment)

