More recently, PRIME II randomised 1326 women aged ≥65 years with ER+, tumour size ≤3cm pN0 tumours to radiotherapy or not, with both groups receiving endocrine therapy. At 5-year median follow-up (IQR: 3.84-6.05) it showed a 1.3% (95%CI: 0.2-2.3) local relapse rate after radiotherapy (n=5) and 4.1% (95%CI: 2.4-5.7) after no radiotherapy (n=26, p=0.002). Consistent with previous studies [15, 16], there was no reported excess of distant relapse, second cancers or deaths illustrating that local relapses can be salvaged with surgery (± radiotherapy) without increasing the risk of breast cancer death (5 year OS 93.9%, CI:91.8-96% in both groups). In an unplanned subgroup analysis, ER-rich patients receiving radiotherapy had only a 2.4% absolute gain in local relapse over non-irradiated patients (local relapse with radiotherapy 0.8% (95%CI: 0.3-1.9) vs 3.2% (95%CI: 2.1-5.2) without radiotherapy). A multivariable analysis for local relapse suggested only use of radiotherapy and oestrogen receptor as independent risk factors (grade non-significant in model). HER2 and Ki67 status was unavailable and there was limited PR data. A larger study is required to confirm the existence and definition of a subgroup with a very low local relapse risk without radiotherapy.

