#### 2.2. Secondary Objectives

- To use immunohistochemical biomarkers with clinical information (IHC4+C) to direct selective avoidance of breast radiotherapy
- To assess the long term disease outcomes following omission of postoperative breast radiotherapy, including:
  - the risk of any ipsilateral invasive and DCIS breast disease by 10 years following omission of postoperative breast radiotherapy
  - the risk of regional and distant relapse by 5 and 10 years following omission of postoperative breast radiotherapy
  - The risk of any ipsilateral breast disease (including non-invasive (DCIS) and invasive ipsilateral disease) by 5 and 10 years following omission of postoperative breast radiotherapy.
  - The risk of contralateral breast second primary cancer by 5 and 10 years following omission of postoperative breast radiotherapy
  - The risk of any contralateral breast disease (including non-invasive (DCIS) and invasive disease) by 5 and 10 years following omission of postoperative breast radiotherapy.
  - The risk of ipsilateral invasive breast local relapse by 5 and 10 years following omission of postoperative breast radiotherapy (subject to availability of tumour profiling data)
  - The risk of ipsilateral invasive breast second primary cancer by 5 and 10 years following omission of postoperative breast radiotherapy (subject to availability of tumour profiling data)
  - o overall invasive disease free survival following omission of postoperative breast radiotherapy
  - breast cancer specific survival following omission of postoperative breast radiotherapy
  - o overall survival following omission of postoperative breast radiotherapy

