## A3. Why is this the preferred design of PRIMETIME?

A cohort based study design is proposed in preference to a randomised controlled trial (RCT) testing breast radiotherapy (RT) versus no RT. Such a design is considered preferable for several reasons:

- (i) The effect of RT in reducing ipsilateral breast disease risk after breast conservation surgery for early breast cancer (rate ratio at 10 years 0.40, SE 0.09) has been fully quantified by RCTs involving 8000 women and >10 years of follow up (1). The proposed design focuses exclusively on testing the *need* for RT in a patient population considered to have such a low risk of local recurrence that the potential absolute gain from RT is considered so small as to not outweigh the established risks associated with breast RT.
- (ii) A review of the worldwide evidence would suppose that within an appropriately defined low risk patient population a cohort of patients treated with surgery and endocrine therapy (as standard) but without RT, would result in local control rates which may be a little higher than what would have been observed if all patients had received RT but given the salvageable nature of such relapses would be expected not to have an adverse impact on long term disease-free and overall survival. Designing a randomised trial to assess such outcomes would result in a trial requiring a large number of patients, with expected challenges associated with randomisation and follow up over many years
- (iii) Conducting a study whereby one defines the limits of acceptability for the upper threshold for 5 year ipsilateral breast disease rate without RT, is deemed preferable and of greater clinical utility by health care practitioners and patient advocates. This concept has been employed previously in breast cancer trials [26]. The concept has also been discussed and developed with UK clinicians and patient advocates, with a recent survey of UK Breast Intergroup members (September 2014) survey showing more than 90% (50/55) support for a case-cohort design. In addition, the case-cohort design has unanimous support from the NCRI Breast Clinical Studies Group (discussed June & November 2014).

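### The endpoint named breast cancer specific survival is defined as a recurrence composite, and no listed endpoint measures breast cancer death alone (Protocol 12.3.2)

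*Protocol*

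**What the plan says.** Section 12.3.2 of the protocol is the only place that defines the endpoint. It opens "Breast cancer specific survival defined as time from registration to first event where event can be local recurrence, regional recurrence, distant recurrence" and ends "breast second primary or breast cancer death. Death from unknown cause would be classed conservatively as breast cancer death". The study summary and sections 2.2 and 4.2 only name it.

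Two neighbouring bullets in 12.3.2 matter for comparison:

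- "Invasive disease free survival defined as time from registration to first event where event can be any invasive local recurrence, regional recurrence, distant recurrence", continuing with second primary cancer and death from any cause.
- "Overall survival defined as time from registration to death from any cause".

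Section 2.2 lists "breast cancer specific survival following omission of postoperative breast radiotherapy" as an objective of its own, beside invasive disease free survival and overall survival. The background in section 1.1, discussing an earlier randomised trial, says that "local relapses can be salvaged with surgery (± radiotherapy) without increasing the risk of breast cancer death". The follow-up part of the study summary plans for "collecting data (including local, distant relapse, new primary cancers, death, cause of death) directly from routinely collected health data".

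**The concern.** Breast cancer specific survival is ordinarily read as freedom from death due to breast cancer. Here the event list makes it a time to first recurrence, new breast primary or breast cancer death. Because only the first event counts, a breast cancer death after a recorded recurrence adds nothing to the estimate.

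Three things follow.

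- **The objective is not answered as named.** The protocol treats breast cancer specific survival as distinct from disease-free and overall survival, but what it would report is a second disease-free measure.
- **Breast cancer death is not isolated anywhere.** The only endpoint that counts deaths alone is overall survival, which mixes all causes. The background separates local relapse from breast cancer death. An endpoint that counts the relapse itself as failure cannot show whether a relapse was salvaged without loss of life.
- **The place of DCIS is unclear.** The bullet on invasive disease free survival restricts local recurrence to invasive disease. The bullet on breast cancer specific survival has no such restriction, so an in-situ event in the breast could count as a survival failure.

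A published figure under this name would naturally be read as breast cancer mortality. Under section 12.3.3 the same definition also carries into the estimates from routine data, including those for women who were pre-screened but not registered.

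**Working it through.** The protocol gives no expected rate, event count or power for this endpoint, so there is no planned figure to reproduce. The check has two parts.

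**1. What each time-to-event endpoint in 12.3.2 counts**

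| Event | Invasive disease free survival | Breast cancer specific survival | Overall survival |
|---|---|---|---|
| Local recurrence | invasive only | yes, not limited to invasive | no |
| Regional or distant recurrence | yes | yes | no |
| Second primary | yes | breast only | no |
| Breast cancer death | yes | yes | yes |
| Death of unknown cause | yes | yes, as breast cancer death | yes |
| Death from another known cause | yes | no | yes |

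No column contains breast cancer death without either recurrences or other deaths. The remaining secondary endpoints are relapse or new-disease rates. The rule for deaths of unknown cause is what one would write for a cause-specific mortality endpoint, so the text may have merged two definitions.

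**2. Size of the difference at 5 years**

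Inputs from section 12.1: 1550 women in the no-radiotherapy cohort; expected ipsilateral rate at most 4%; 5% as the rate to be excluded; 5% non-evaluable. The 2% and 3% rates are assumptions, used to show the range.

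Let *r* be the 5-year ipsilateral rate. If every ipsilateral event counts as a local recurrence or a breast second primary:

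- women failing from ipsilateral events ≈ 1550 × *r*;
- highest possible reported value ≈ 1 − *r*, even with no breast cancer deaths.

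| *r* | Source | 1550 × *r* | Ceiling 1 − *r* |
|---|---|---|---|
| 2% | assumed | 31 | 98% |
| 3% | assumed | 46.5 | 97% |
| 4% | top of expected range | 62 | 96% |
| 5% | rate to be excluded | 77.5 | 95% |

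With 5% non-evaluable, the 4% row becomes 1550 × 0.95 × 0.04 = 58.9 women, and the ceiling does not change.

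The gap from a mortality-based figure is smaller than *r* when some ipsilateral events do not count or are followed by breast cancer death. Let *d* be the share that is DCIS, if DCIS is not counted. Let *q* be the share of the remaining women who die of breast cancer within 5 years. Then the gap due to ipsilateral events ≈ *r* × (1 − *d*) × (1 − *q*). The protocol gives neither *d* nor *q*, so *r* is the upper limit of this part of the gap. Regional, distant and contralateral events add to it, and the protocol gives no rates for them.

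**The case against.** The strongest reply is that the event list is written out in full, so a careful reader can see what is counted. It is also one secondary endpoint among ten, with no hypothesis or decision rule, and section 12.4 rules out formal comparison between the cohorts. Interim monitoring under 12.5 uses ipsilateral invasive disease. All of this stands. It limits the seriousness, but it does not make the name, the objective and the event list agree.

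Several stronger readings are tempting and are not supported:

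- *That the figure is at least 4 points too low.* Section 12.1 expects at most 4%, and that rate includes DCIS. Four points is therefore an upper limit for the ipsilateral part at the expected rate.
- *That the total is 6 to 8 points.* This adds an assumed 2% to 4% for other events and ignores women who have more than one type of event, while the composite counts only the first.
- *That in-breast events dominate the composite.* With 4% ipsilateral and 4% other events they would be half, and the second figure is an assumption.
- *That the design rationale rests on this endpoint.* Appendix A3 (ii) says that salvageable relapses "would be expected not to have an adverse impact on long term disease-free and overall survival". Both outcomes have their own endpoints. Only the background in 1.1 speaks of breast cancer death.
- *That the results could not be pooled.* The meta-analysis in 12.6 is described in A3 (vi) as using individual patient data, so endpoints can be derived again there.

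**Conclusion.** The definition in 12.3.2 does not match its name or the objective in 2.2, and no listed endpoint measures breast cancer death alone. At the expected ipsilateral rate of at most 4%, ipsilateral events could lower the reported 5-year value by up to about 4 percentage points, or about 2 to 3 points at assumed rates of 2% to 3%. This assumes that all ipsilateral events count and that none of these women die of breast cancer by 5 years; if either fails, the effect is smaller. Other recurrences and contralateral primaries lower the value further by an unknown amount.

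The error makes omission of radiotherapy look worse, not better. A reader might infer that breast cancer mortality could not be recovered, but cause of death is planned through routine data, so the gap lies in the definition. The primary endpoint, the target of 1550 and interim monitoring are untouched. The point should be fixed, but it does not threaten the main conclusion of the trial.

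**What to change.** In section 12.3.2:

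1. Define breast cancer specific survival as time from registration to death from breast cancer, and keep the existing rule that a death of unknown cause counts as one.
2. Keep the present composite as a separate endpoint under its own name, for example breast-cancer-free interval, and state whether DCIS counts as local recurrence in it.
3. Carry both names into the study summary and sections 2.2 and 4.2, so that the objectives and endpoint lists agree.

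How deaths from other causes are handled can be left to the statistical analysis plan.

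The cost is a wording amendment. Sites already report relapse, new primary disease and death, and cause of death is planned through linkage. Linkage depends on patient consent (8.5.3), so it is worth confirming that the case report form also records cause of death.
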